#### 8.5 Treatment planning

##### Treatment technique

The radiation treatment can be given with protons or photons (3DCRT/IMRT/VMAT).

## Dose computation and optimization

Dose calculation	Reference dosimetry is carried out according to the IAEA report TRS 398 (2000).  The absorbed dose in the patient geometry shall be calculated by using validated algorithms.  The calculation grid shall be at maximum 3 mm.
------------------	-------------------------------------------------------------------------------------------------------------------------------------------------------------------------------------------------------------------------------------------

In order to facilitate the optimization procedure, help structures and volumes may be defined.

For proton treatments, see treatment planning and optimization guidelines in the Skandion Clinic treatment planning instruction manual (Delprocess 5 / Gör dosplanering och QA-plan och godkänn dosplan / Dosplaneringsmanual)

## Treatment plan evaluation

A robustness test should be performed for each proton treatment in 12 test cases according to the recommendations in the Skandion Clinic treatment planning instruction manual (Delprocess 5 / Gör dosplanering och QA-plan och godkänn dosplan / Dosplaneringsmanual). Tolerance levels that should be fulfilled in the robustness test for treatments with the prescribed doses are described in table 2

**Table 3. Tolerance levels that should be fulfilled in the robustness test. RBE value/model 1.10 is used.**

Tolerance levels	
CTV: all test cases	$D_{98\%} \geq 90\%$
CTV: for at least 10 of 12 robustness test cases	$D_{98\%} \geq 95\%$
GTV: all test cases	$D_{95\%} \geq 100\%$
GTV: for at least 10 of 12 robustness test cases	$D_{98\%} \geq 100\%$
Spinal cord: all test cases	$V_{48 \text{ Gy (RBE)}} \leq 100\%$

DVH parameters of OARs used for definition of objectives and constraints (table 2)	According to clinical judgement
------------------------------------------------------------------------------------	---------------------------------

---

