## 8.3 Doses to organs at risk

- Spinal cord

The maximum dose to the spinal cord is 48 Gy EQD2. The spinal cord shall be defined as the content of the spinal canal.

- Lung

Normal lung tissue is to be spared as much as possible. The volume of the lung (minus GTV) that should not receive doses above 20 Gy should be  $\leq 35\%$  ( $V_{20} < 35\%$ ). Dose-volumes histograms should be performed and the percentage of the lung volume minus GTV receiving a dose  $>5$ ,  $>20$  and  $>40$  Gy as well as mean lung dose shall be recorded ( $V_5$ ,  $V_{20}$ ,  $V_{40}$ , MLD)

- Esophagus

The esophagus shall be delineated from the esophageal entrance to cardia. The mean dose should be  $< 45$  Gy EQD2. The mean dose as well as the volume of the esophagus receiving  $> 50$  Gy EQD2 ( $V_{50}$ ) shall be recorded.

- Heart

The whole heart shall be delineated including the atriums and chambers but not the great vessels. No constraint is used, but the aim is to keep the dose as low as possible. Mean dose and volume receiving  $> 10$  Gy EQD2,  $> 20$  Gy EQD2 and  $> 40$  Gy EQD2 (MHD,  $V_{10}$ ,  $V_{20}$ ,  $V_{40}$ ) shall be recorded.

- LADCA

LADCA (Left Anterior Descending Coronary Artery) shall be delineated. No constraint will be used but  $D_{2\%}$  and  $D_{mean}$  shall be recorded

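### The spinal-cord tolerance in Table 3 is met by every dose distribution, so the robustness table does not carry the 48 Gy cord maximum set elsewhere in the protocol

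*Protocol*

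**What the plan says.** Table 3 lists the levels that the proton plan should meet in the robustness test. Four lines concern the CTV and GTV. One line concerns the cord: "Spinal cord: all test cases", with the tolerance "V_{48 \text{ Gy (RBE)}} \leq 100" percent. A final row covers the organ-at-risk parameters of Table 2, and its entry is "According to clinical judgement".

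The V notation is explained in section 8.3. For lung it is "the percentage of the lung volume minus GTV receiving a dose" above 5, 20 or 40 Gy, and heart V10, V20 and V40 are described in the same way. Section 8.3 also gives the cord limit: "The maximum dose to the spinal cord is 48 Gy EQD2". Table 2 (section 8.4) ranks the cord as priority 1, at 48 Gy(RBE) or 43.64 Gy physical dose. Section 8.0 requires that every included patient can receive the prescribed dose without exceeding the organ-at-risk doses.

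Two places direct the reader to a tolerance table. Under the heading Treatment plan evaluation, section 8.5 says: "Tolerance levels that should be fulfilled in the robustness test for treatments with the prescribed doses are described in table 2". Section 8.6, on image-guided and adaptive delivery, instead cites Table 3 when it describes the possibility of re-planning after a control CT.

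**The concern.** The robustness cases and control CTs exist to reveal what set-up error, range error or changed anatomy does to a plan that looked acceptable at the start. For that purpose each tolerance line has to be one that a bad case can fail. The CTV and GTV lines can be failed. The cord line cannot, although the cord is the organ that Table 2 places first. The remaining organ row has no number of its own. Someone working from Table 3 alone therefore has no numeric cord threshold and must either fetch it from section 8.3 or Table 2 or decide by judgement.

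**Working it through.** **Inputs.** From the protocol: the Table 3 cord line; the meaning of V in section 8.3; the cord maximum of 48 Gy EQD2 (section 8.3) and 48 Gy(RBE) (Table 2); RBE 1.1; 12 test cases; prescriptions of 50, 57.5 and 62.5 Gy(RBE) at 2, 2.3 and 2.5 Gy(RBE) per fraction (section 5.3). Assumed, because the protocol gives no value: alpha/beta for the cord of 2, with a range of 1 to 3.

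**Step 1: the intended dose level.** 48 / 1.1 = 43.64 Gy, which reproduces the physical dose in Table 2. The 48 in Table 3 is therefore the same limit, and the fault lies in the comparison with 100%.

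**Step 2: can the printed line fail?** V48 = 100 × (cord volume above 48 Gy(RBE)) / (total cord volume). The numerator is part of the denominator, so V48 lies between 0% and 100% for any distribution, and V48 ≤ 100% always holds. Some uniform cord doses show the contrast:

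| Uniform cord dose, Gy(RBE) | As printed, V48 ≤ 100% | As a maximum, Dmax ≤ 48 |
|---|---|---|
| 0 | pass | pass |
| 48 | pass | pass |
| 62.5 | pass | fail |
| 100 | pass | fail |
| 1000 | pass | fail |

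Reading V48 as a dose of at least 48 rather than above 48 changes nothing in the printed column.

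**Step 3: would a correct line have content in every dose group?** 48/50 = 96.0%; 48/57.5 = 83.5%; 48/62.5 = 76.8%. The limit lies below the prescription in all three groups, so a line set at 48 Gy(RBE) could be failed in each. This says nothing about how often it would be, since the documents hold no cord dose data.

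**Step 4: does Dmax ≤ 48 Gy(RBE) respect section 8.3?** Section 8.3 is in EQD2, so a conversion is needed. Every group has 25 fractions (50/2 = 57.5/2.3 = 62.5/2.5 = 25), and 48/25 = 1.92 Gy(RBE) per fraction. EQD2 = D × (d + alpha/beta) / (2 + alpha/beta):

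- alpha/beta 2: 48 × 3.92 / 4 = 47.04
- alpha/beta 1: 48 × 2.92 / 3 = 46.72
- alpha/beta 3: 48 × 4.92 / 5 = 47.23

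All are below 48 Gy EQD2. In the other direction, solving D × (D/25 + 2) / 4 = 48 gives D = 48.65 Gy(RBE) (48.79 for alpha/beta 1, 48.56 for 3). The proposed line is thus 0.6 to 0.8 Gy(RBE) stricter than section 8.3, not looser.

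**The case against.** The strongest reply is that the limit is already in force. Section 8.0 forbids exceeding organ-at-risk doses, section 8.3 states the cord maximum, and Table 2 puts it first. None of these is restricted to the nominal plan, so a planner who sees more than 48 Gy in a test case already has a stated limit. This stands, and it limits the point to Table 3.

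A second reply is that section 8.5, taken at its word, sends the reader to Table 2, where the cord limit is 48. If that reference is treated as a slip, the cord line deserves the same charity and can be read as a maximum of 48 Gy(RBE). That is probably what was meant. But the title of Table 3 and the citation in section 8.6 both identify Table 3 as the robustness table. Taken literally, the reference to Table 2 also clashes with the last row of Table 3, which applies the Table 2 parameters only by judgement. Both slips need correcting.

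Third, the test is run "according to the recommendations in the Skandion Clinic treatment planning instruction manual". That manual is not in the documents and may hold a proper cord criterion. This also stands: the practical effect cannot be judged from the protocol.

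A misread symbol in the extracted table cannot be wholly excluded, but the cord line reads cleanly and shows no sign of a broken cell.

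A reader might infer that the protocol leaves the cord unprotected, or lets it receive the full prescription. The documents do not support that, because section 8.3 bars such a dose. Nor do they support saying that a mandatory re-plan trigger is disabled: section 8.6 offers re-planning only as a possibility, and the target lines of Table 3 still work.

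**Conclusion.** The Table 3 cord line is wrong as printed: 0 of 12 test cases can fail it. That conclusion follows from the protocol's own V notation and needs no assumption about radiobiology. It concerns a decision threshold for the priority 1 organ, in the table used for robustness testing and cited for the control-CT check, so it deserves correction even though it is probably a notation slip.

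Its reach is narrow. The 48 Gy maximum applies through other sections, the effect on actual plans is unknown, and no sample size, endpoint or analysis depends on it. Only the statement that the replacement is no looser than section 8.3 rests on the assumed alpha/beta, and it holds across the range 1 to 3.

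**What to change.** Replace the cord tolerance in Table 3 with: spinal cord Dmax ≤ 48 Gy(RBE) in all test cases. Section 8.8 already has the cord Dmax recorded, so no new quantity is needed. A near-maximum such as D2% should not be used here, although it is recorded elsewhere: D2% ≤ 48 would let up to 2% of the cord exceed 48 Gy and so be looser than the maximum the line is meant to match.

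In section 8.5, under Treatment plan evaluation, change the reference for the robustness tolerances from Table 2 to Table 3.

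The cost is one table line and one cross-reference. A few plans may need adjusting, namely those whose cord maximum exceeds 48 Gy(RBE) in some test case.

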## **8.6 Patient monitoring before and during treatment**

Before treatment starts patients will undergo a control 4D-CT at Skandion Clinic. If tumour motion exceeds 0.5 cm proton treatment will not be given and patient will receive the photon backup plan instead.

### Image guided and adaptive treatment delivery

The position of the patient shall be verified based on MV imaging, CBCT, kV imaging and/or surface imaging.

For photons, the position of the patient shall be verified daily, or at least the first 3 days and then weekly during the treatment. A statistical analysis shall be performed after the first 3 treatments. Based on the analysis, the treatment delivery shall be adapted according to protocol for corrective action.

For protons daily imaging is required. Patient weight will be controlled once a week. If weight loss/gain > 5% a control CT will be performed at Skandion Clinic, otherwise control CT will be performed weekly with the possibility to re-plan if the difference between the dose distribution of the original treatment plan and the dose distribution based on this new CT is not in accordance with the tolerance levels specified for the robustness test (see table 3).

## **8.7 Interruption of radiotherapy**

After radiotherapy starts, efforts should be made to avoid interruptions in the planned schedule. If an interruption must be made due to technical or administrative reasons the following policy will be applied. At least four fractions a week must be given. If this is not possible with protons the photon backup plan must be used. Try to maintain the total treatment time as close to 5 weeks as possible.

## **8.8 Quality assurance**

The absorbed dose to the patient shall be estimated based on in vivo measurements according to clinical routine procedures. If in-vivo dosimetry is not applicable, pre-treatment patient specific quality assurance (QA) must be performed.

Treatment plan parameters should be recorded for quality assurance purposes. The volume of GTV and PTV should be registered as well as dose/volume-parameters to organs at risk: Lung: V5, V20, V40, MLD. Esophagus: V60, V80, mean dose. Heart: V10, V20, V40, mean dose, Spinal cord: Dmax.

## **9 Adverse events**

### **9.1 Definition**

#### **Adverse events (or adverse experience) (AE):**

An AE is any untoward medical occurrence in a subject or clinical investigation subject treated within a study protocol and which does not necessarily have a causal relationship with this treatment.

An AE can therefore be any unfavorable and unintended sign (including an abnormal laboratory finding, for example), symptom, or disease temporally associated with the radiation treatment, whether or not considered related to the radiotherapy

Due to regulatory requirements, events occurring during pre- and post-treatment periods should also be designated as AEs. Therefore, safety surveillance - reporting of (S)AEs - commences at the time when the subject is enrolled into the study (date of signature of the informed consent) until the End of Study Visit has been performed.

#### **Serious adverse event or reaction/experience (SAE):**

- A serious AE (experience) or reaction is any untoward medical occurrence that at any dose:
- Results in death
- Is life-threatening
- **NOTE:** The term "life-threatening" in the definition of "serious" refers to an event in which the subject was at risk of death at the time of the event; it does not refer to an event which hypothetically might have caused death if it were more severe.
- Requires in-patient hospitalization or prolongation of existing hospitalization
- Results in persistent or significant disability/incapacity

- Is a congenital anomaly/birth defect or
- Is an important medical event

Medical and scientific judgment should be exercised in deciding whether expedited reporting is appropriate in cases of important medical events that may not be immediately life-threatening or result in death or hospitalization but may jeopardize the subject or may require intervention to prevent one of the other outcomes listed in the definition above. These should also usually be considered serious.

Examples of such events are intensive treatment in an emergency room, or at home for allergic bronchospasm; blood dyscrasias or convulsions that do not result in hospitalization; or development of drug dependency or drug abuse, or malignant tumors when they are histologically different from the primary tumor.

### **Events not to be treated as SAEs**

Progression of disease is not to be regarded as a SAE.

Due to the seriousness of the disease in this study, certain conditions defined as SAEs will be excluded from expedited reporting on a SAE report form:

- Elective hospitalization and surgery for treatment of disease
- Elective hospitalization to simplify treatment or study procedures

## **9.2 Recording of Adverse Events**

All AEs must be documented in the appropriate section of the CRF. For SAEs, a SAE report form (initial or follow up) must be completed in addition.

The following aspects must be recorded for each event in the CRF:

- A description of the AE in medical terms, not as reported by the subject;
- The date of onset (start date)
- The date of recovery (stop date)

At each contact with the subject, the investigator must seek information on adverse events by specific questioning and, as appropriate, by examination. Information on all adverse events should be recorded immediately on the Adverse Event module of the CRFs using the CTCAE Version 4.0

A written version will be available at each study site, see also. CTCAEv4.0.

Version 4.0 <http://ctep.cancer.gov/reporting/ctc.html>

Serious adverse events should be noted on the Serious Adverse Event Report form.

All adverse events occurring during the study period must be recorded. The clinical course of each event should be followed until resolution, stabilisation or until it has been determined that study treatment or participation is not the cause. Serious adverse events, which are still ongoing at the end of the study period, must be followed up to determine the final outcome.

Any serious adverse event, which occurs after the study period and is considered to be possibly related to study treatment or study participation should be recorded and reported immediately.

The grade as assessed by the investigator according to the definitions in CTCAE v4.0.

Grade 1 = mild

Grade 2 = moderate

Grade 3 = severe

Grade 4 = life-threatening or disabling

Grade 5 = death related to AE

- The causal relationship to therapy as assessed by the investigator; the decisive factor in the documentation is the temporal relation between the AE and the study drug. The following judgments of the causality to study procedures are to be used:

**Not Related**; There is not a temporal relationship to study treatment.

**Not Likely**; There is a temporal relationship to study treatment, but there is not a reasonable causal relationship between the treatment and the AE.

**Possible**; there is a reasonable causal relationship between the study treatment and the AE.

**Probable**; there is a reasonable causal relationship between the study treatment and the AE.

**Certain/Definite**; there is a reasonable causal relationship between the study treatment and the AE. Action taken (none, treatment discontinued, dose reduction, treatment delayed, concomitant medication given, new or prolonged hospitalization, procedural surgery).

- The outcome according to the following definitions:

- Recovered with sequelae.
- Recovered without sequelae.
- Ongoing, no therapy.
- Ongoing, therapy.
- Died.
- Change in toxicity grade/severity.
- Seriousness: yes or no
- In case of SAEs it must be indicated whether the SAE is the leading event, i.e. the primary medical reason for SAE reporting.

### **9.3 Reporting of Serious Adverse Events**

In the event of the occurrence of any clinical AE or abnormal laboratory test value that is serious or medically important during the course of the study or the post-treatment period, irrespective of the treatment received by the subject, the co-investigator is obliged to immediately inform the Investigator-Sponsor.

The immediate report by the co-investigator to the Investigator shall be followed by detailed, written reports using the SAE report form (for an “initial” SAE or for “follow-up” information on a previous SAE). The immediate and follow up reports shall identify subjects by unique code numbers assigned to the latter.

For names, addresses, telephone and fax numbers, see below.

If the adverse event is life-threatening or results in death it should be recorded and reported as soon as possible or within 7 days and for all other suspected serious unexpected adverse reaction shall be recorded and reported as soon as possible but within a maximum of fifteen days of the first knowledge. The Investigator shall ensure that for a reported death of a subject, the investigator shall supply the Ethics Committee with any additional information as requested.

A copy of the reports to the Regulatory Authorities and Ethics committees should be sent to the Investigator (principal investigator), [name] [contact].

Annually throughout the clinical trial, the Investigator shall provide the local Regulatory Authority, Ethics committee, with a listing of all suspected serious adverse reactions which have occurred over this period and a report of the subject’s safety.

The finally listing and report will be 60 days after data-lock point.

#### **9.4 Monitoring of subjects with adverse events**

Any AE that occurs in the course of a clinical study must be monitored and followed up until the End of Study Visit. In addition SAEs must be reported via a SAE report form (see section 9.3 Reporting of serious adverse events).

It is the responsibility of the investigator that any necessary additional therapeutic measures and follow-up procedures are performed.

#### **9.5 Patient Removal from Study Therapy due to Adverse Events**

Any subject who experiences an adverse event may be withdrawn at any time from the study at the discretion of the investigator.

If a subject is withdrawn wholly or in part because of an adverse event, this should be noted on the Study treatment form in addition to the Adverse Event section. The monitor should be informed without delay of all subjects who are withdrawn for this reason.

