#### **4.1.1 Primary Objective**

Toxicity (eg cardiac and pulmonary toxicity).

Local control at 5 years. Local control is defined as freedom of locally progressive disease; ie CR (complete remission) or SD (stable disease) based on CT or PET/CT evaluation

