## **5.6 Follow-up**

First follow-up 4 weeks after completion of therapy, then at four months and every three months thereafter for the first year, then every six months for a maximal five years in total.

Recording of persistent or new toxicity, performance status and weight will be done at all visits.

Tumour response evaluation with CT scan will be done at 4, 7, 10 and 13 months after therapy and every 6 months thereafter or if clinically indicated.

Quality of life according to QLQ30 + LC 14 will be measured at baseline, week 3 during treatment, and of treatment, 1, 3, 6 and 12 months after completion of radiotherapy. Thereafter at 2, 3 and 5 years after treatment. The administration of the questionnaires will be handled centrally by the Clinical Trial Unit at the Oncology Department, Sahlgrenska University Hospital.

Spirometry including CO diffusion capacity will be repeated at 6 months after therapy and at end of study

UCG will be performed within two weeks after completion of therapy and at end of study, i e 5 years after treatment

ECG will be recorded at each visit

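### Section 9.5 permits withdrawal from the study, not only from radiotherapy, after any adverse event, and nothing secures later toxicity and local-control data in patients so withdrawn

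*Protocol*

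**What the plan says.** The heading of protocol section 9.5 is "Patient Removal from Study Therapy due to Adverse Events". The sentence beneath it says something wider: "Any subject who experiences an adverse event may be withdrawn at any time from the study at the discretion of the investigator". The section then asks that a withdrawal caused by an adverse event be noted on the treatment form and in the adverse event section, and that the monitor be told promptly.

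Section 9.4 states: "Any AE that occurs in the course of a clinical study must be monitored and followed up until the End of Study Visit". Section 9.2 asks that each event be followed until it resolves, stabilises or is judged unrelated to the study. Section 9.1 runs safety surveillance from consent to the End of Study Visit. Section 5.5 lists reasons for stopping treatment; its adverse-reaction item covers severe or life-threatening reactions that rule out further treatment.

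Both primary objectives in section 4.1.1 need long observation: "Toxicity (eg cardiac and pulmonary toxicity" and "Local control at 5 years". Section 5.6 schedules visits, "then every six months for a maximal five years in total", and adds: "Recording of persistent or new toxicity, performance status and weight will be done at all visits". On the cardiac assessment it says: "UCG will be performed within two weeks after completion of therapy and at end of study, i e 5 years after treatment". Spirometry is also repeated at end of study.

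**The concern.** Treatment is planned to last five weeks and follow-up 60 months. A rule allowing withdrawal from the study at any time therefore applies mostly to patients who have no radiotherapy left to stop. Read literally, its only effect on them is to end observation, and what triggers it is an adverse event, in a trial where toxicity is a primary endpoint.

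If patients with early toxicity have a different risk of late toxicity from the others, losing them makes the observed late rate unrepresentative of the treated group. Section 3.0 describes radiation-induced heart disease as mainly a late effect, so the data most exposed are those due last: late toxicity visits, the 5-year echocardiogram and the end-of-study spirometry. A withdrawn patient also leaves the 5-year local control assessment.

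**Working it through.** **1. The texts side by side (protocol)**

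| Section | Trigger | What ends or continues |
|---|---|---|
| 9.5 heading | adverse event | study therapy ends |
| 9.5 sentence | any adverse event, any time, investigator's choice | participation in the study ends |
| 5.5 | severe or life-threatening reaction | treatment ends |
| 9.4 | any adverse event | follow-up of that event continues to the End of Study Visit |
| 9.2 | any adverse event | follow-up of that event continues to resolution, stabilisation or a finding of no causal link |

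The 9.5 sentence agrees with neither its heading nor 5.5, on what is stopped and on which events justify it. Against 9.4 the conflict is partial. Section 9.4 requires follow-up of an event that has occurred. It does not require the remaining scheduled assessments in a patient who has left the study.

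**2. Does another section keep such patients in follow-up?** None says so. Section 5.7 calls the discontinuations of 5.5 dropouts. Section 5.8 defines completion by evaluable patients who completed treatment and were followed for 60 months. Both make it easier to read a withdrawn patient as gone.

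**3. Share of study time affected.** Sixty months is about 5 × 52 = 260 weeks. With five weeks of radiotherapy, follow-up makes up 260/265 = 98% of the time from start of treatment.

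**4. Scale.** The protocol gives no adverse event rate, late-toxicity rate or withdrawal rate. Apart from N = 40, every input here is an assumption. Let *a* be the share with an early adverse event, *p₁* and *p₀* the late-toxicity risk with and without one, and *w* the share of early-event patients withdrawn, unrelated to late risk within that group.

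- True rate = a·p₁ + (1 − a)·p₀
- Rate among those followed = [a(1 − w)p₁ + (1 − a)p₀] / (1 − a·w)
- Patients lost = 40·a·w

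With p₀ = 10%:

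| a | p₁ | w | Lost of 40 | True | Observed | Shortfall (points) |
|---|---|---|---|---|---|---|
| 25% | 20% | 20% | 2 | 12.5% | 12.1% | 0.4 |
| 25% | 40% | 50% | 5 | 17.5% | 14.3% | 3.2 |
| 50% | 30% | 20% | 4 | 20.0% | 18.9% | 1.1 |
| 50% | 30% | 50% | 10 | 20.0% | 16.7% | 3.3 |
| 50% | 40% | 50% | 10 | 25.0% | 20.0% | 5.0 |

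First row: (0.25 × 0.8 × 0.20 + 0.75 × 0.10)/(1 − 0.05) = 0.115/0.95 = 12.1%. Last row: (0.5 × 0.5 × 0.40 + 0.5 × 0.10)/(1 − 0.25) = 0.15/0.75 = 20.0%. If p₁ = p₀ there is no bias, and if p₁ < p₀ the sign reverses.

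**5. Bounds without a risk model.** Suppose 4 late events are seen and *m* patients are withdrawn. The rate in all 40 lies between 4/40 and (4 + m)/40: 10–15% for m = 2, 10–20% for m = 4 and 10–30% for m = 8.

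**The case against.** The strongest reply is that 9.5 means therapy and uses the word study loosely. Its heading says therapy, and its next sentence sends the record to the treatment form. The rule is permissive, while 9.4 is mandatory. This may well be a drafting slip, and that stands as an account of intent. It does not remove the problem, because the operative sentence still permits study withdrawal and no other section says that follow-up continues.

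Several stronger readings are tempting but are not supported:

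- *That the triggering toxicity goes unmeasured.* Sections 9.2 and 9.4 require that event to be recorded and followed. The exposure is later, new toxicity, the end-of-study tests and local control.
- *That the bias favours protons.* Even against historic data this needs early-event patients to carry a higher late risk, which is assumed. The synopsis has photon patients followed on the same plan, and 9.5 speaks of any subject, so loss could occur in both groups. The text gives no direction for that comparison.
- *That analysis cannot address it.* Section 9.5 requires these withdrawals to be documented, so the patients can be identified and bounds calculated as in step 5. Analysis cannot recover visits that were not made, but how missing data are handled may be set out in an analysis plan not seen here.
- *That the bias is large.* At N = 40 and a 20% rate, the sampling standard error is √(0.2 × 0.8/40) = 6.3 points, more than any shortfall in the table.

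**Conclusion.** The concern holds as an internal conflict that leaves a gap in data retention. The 9.5 sentence disagrees with its heading, with 5.5 and in part with 9.4, and it permits a loss that depends on toxicity, a primary outcome. That loss may be informative. The conclusion rests on the wording alone and needs no numerical assumption.

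The size cannot be derived from the protocol. The 0.4 to 5 point range depends wholly on assumed rates and on early-event patients having the higher late risk. The bounds show that, with 40 patients, each lost patient widens the possible range by 1/40 = 2.5 points. The point merits correction because the data at risk cannot be collected afterwards, not because a large bias has been shown.

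**What to change.** Reconcile the 9.5 sentence with its heading, with 9.4 and with 5.5. When radiotherapy should stop is for the investigators to settle; this review proposes no rule on it.

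Separately, add a statement on follow-up to this effect: patients whose study treatment is stopped, or who have an adverse event, remain in the study for all scheduled assessments to 60 months unless they withdraw consent, and are included in the analysis. List the assessments: toxicity, cardiac, lung function, imaging as in Table 1, quality of life and survival. Keep the reference to Table 1 for imaging, because its first note allows CT to end at progression.

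The cost is one amendment. The visits and tests are already in the schedule.
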